6.2 Secondary Objectives

The secondary objectives of this study are:

- To evaluate the efficacy of treatment with IFN-K using:
 - The SLE Responder Index [(SRI)-4 and above]
 - The SLE Disease Activity Index-2000 index (SLEDAI-2K)

- The BILAG-2004 index
- The Safety of Estrogen in Lupus Erythematosus National Assessment-SLEDAI (SELENA-SLEDAI) Flare index
- The Systemic Lupus International Collaborating Clinics/American College of Rheumatology Damage Index for Systemic Lupus Erythematosus (SLICC/ACR-DI)
- The Cutaneous Lupus Erythematosus Disease Area and Severity Index (CLASI) in patients with cutaneous lesions at baseline
- To evaluate the immune response induced by IFN-K:
 - Anti-IFN α antibody response
 - Anti-IFN α antibody neutralizing capacities
 - Anti-KLH antibody response
- To assess the safety of IFN-K emulsified with ISA 51 VG

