2.2.2 Secondary objectives

The secondary objectives of this study are:

- To evaluate the efficacy of treatment with IFN-K using:
 - The SLE Responder Index [(SRI)-4 and above]
 - The SLE Disease Activity Index-2000 index (SLEDAI-2K)
 - The BILAG-2004 index
 - The Safety of Estrogen in Lupus Erythematosus National Assessment-SLEDAI (SELENA-SLEDAI) Flare index
 - The Systemic Lupus International Collaborating Clinics/American College of Rheumatology Damage Index for Systemic Lupus Erythematosus (SLICC/ACR-DI)
 - The Cutaneous Lupus Erythematosus Disease Area and Severity Index (CLASI) in patients with cutaneous lesions at baseline
- To evaluate the immune response induced by IFN-K:

Statistical Analysis Plan

Study Name: IFN-K-002

SAP version & date: v4, 18/Jun/2018

- Anti-IFN α antibody response
- Anti-IFN α antibody neutralizing capacities
- Anti-KLH antibody response
- To assess the safety of IFN-K emulsified with ISA 51 VG

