3.3 Analysis dataset definitions

3.3.1 Full Analysis Set (FAS)

The primary efficacy analysis population is the Full Analysis Set (FAS). It will include all randomized patients who received at least one dose of the study product (IFN-K or placebo). This population will be analyzed according to the result of the random treatment assignment.

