4.1.2 Secondary efficacy endpoints

4.1.2.1 Clinical Secondary Endpoints

- Response to treatment with IFN-K, as measured by the SLE Responder Index (SRI)-4 response criteria at Week 36:
 - Reduction \geq 4 points in SELENA-SLEDAI at week 36 compared with baseline
and
 - No new BILAG A at Week 36
and
 - No more than 1 new BILAG B at Week 36
and
 - No deterioration at Week 36 in PGA (< 10% worsening) on VAS 100 mm compared with baseline
- Response to treatment with IFN-K, as measured by the composite SLE Responder Index (SRI)-4 response criteria at Week 36:
 - Same criteria as above
and
 - Sustained reduction in oral corticosteroids (\leq 5 mg and \leq 7.5mg/day) at Week 36 (these criteria will be identified by medical review)
- Response to treatment with IFN-K, as measured by SLEDAI response, defined as a reduction of the SLEDAI-2K score of at least 4 points at Week 36 compared to baseline
- Response to treatment with IFN-K, as measured by BILAG grade changes by body system
- Response to treatment with IFN-K, as measured by Incidence of SLE flare (SELENA SLEDAI flare index. BILAG flares)
- Response to treatment with IFN-K, as measured by SLICC/ACR-DI
- Response to treatment with IFN-K, as measured by Cutaneous LE Disease Area and Severity Index (CLASI)
- Response to treatment with IFN-K, as measured by LLDAS (Franklin *et al*, 2016)

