5.2.4.3 Secondary efficacy analyses

Secondary efficacy analyses will be performed on the FAS population except if otherwise specified.

5.2.4.3.1 *SRI response*

The SRI-4, 6, 8, 10 responses will be described at Week 36. (Statistical tables 14.2.5.1, 14.2.5.4, 14.2.6.1, 14.2.7.1, 14.2.8.1)

The SRI-4 response (section 4.1.2.1) will be analyzed using the same method as the primary analysis for the second co-primary endpoint (logistic regression). This analysis will be performed both on the FAS and PP sets. (Statistical tables 14.2.5.2 & 14.2.5.5)

The model on FAS for patients IFN-K treated with the status of IFN α neutralizing antibodies (positive/negative) at Week 36 as dependent variable will be also presented (Statistical table 14.2.5.3).

The SRI-6, 8, 10 responses to treatment at week 36 will also be analyzed using a logistic regression using the response rate as dependent variable and treatment as independent variable, while adjusting for the minimization factors used for randomization. (Statistical tables 14.2.6.2, 14.2.7.2, 14.2.8.2)

All analyses performed on SRI-4 will also be conducted on the composite SRI-4 (both with tapering CS \leq 5 mg and \leq 7.5 mg) on the FAS population only. (Statistical tables 14.2.5.6 to 14.2.5.11)

The SRI-4 response is an important and alternative endpoint assessing the clinical response. In case, there will be no trend on the BICLA response, the SRI-4 response could be chosen as primary endpoint for further development of IFN-K.

5.2.4.3.2 *SLEDAI response*

Number of patients achieving a SLEDAI response, defined as a reduction of the SLEDAI-2K score of at least 4 points at Week 36 compared to baseline will be analyzed using frequency table methods (Statistical table 14.2.9).

SLEDAI-2K score at each visit and change from baseline by treatment group will also be presented (Statistical tables 14.2.10.1 to 14.2.10.2).

All SLEDAI data will be listed in Listing 16.2.6.2.

5.2.4.3.3 *BILAG*

Shift tables between Baseline and LVA (last available value between Week 36 and Week 24) will also be presented for each body system. (Statistical table 14.2.11)

Finally, descriptive statistics for the BILAG global score at each visit and change from baseline to LVA will be presented. The difference between treatment groups for the change from baseline to LVA will be analyzed using the non-parametric Wilcoxon-test. (Statistical table 14.2.12)

Statistical Analysis Plan

Study Name: IFN-K-002

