SAP version & date: v4, 18/Jun/2018

The BILAG global score will be defined as the summation of the numerical values for the nine-system scores as given by the following formula:

$$\text{Numerical global score (xs)} = A*12 + B*8 + C*1$$

Where A, B and C represent the number of Grades A, B and C respectively at each assessment. Grades D and E are considered as 0 (Chee-Seng Yee *et al*, 2010).

All BILAG data will be listed in Listing 16.2.6.3.

5.2.4.3.4 *SELENA SLEDAI flare index*

The numbers of patients with a mild or moderate, or severe SLE flare (SELENA-SLEDAI flare index) and corresponding number of SLE flare will be presented. (Statistical table 14.2.13).

The total score at each visit (planned in the protocol) and change from baseline by treatment group will also be presented. The change at Week 36 will be analyzed using a t-test. (Statistical tables 14.2.14.1 to 14.2.14.2).

All SELENA-SLEDAI flare index data will be listed in Listing 16.2.6.4.

5.2.4.3.5 *SLICC/ACR-DI*

Total score at each visit and change from baseline by treatment group will be presented. The change at Week 36 will be analyzed using a t-test. (Statistical tables 14.2.15.1 to 14.2.15.2).

All SLICC/ACR-DI data will be listed in Listing 16.2.6.5.

5.2.4.3.6 *CLASI*

Total activity score and Total damage score at each visit and change from baseline by treatment group will also be presented. The changes at Week 36 will be analyzed using a t-test. (Statistical tables 14.2.16.1 to 14.2.17.2).

All CLASI data will be listed in Listing 16.2.6.6.

5.2.4.3.7 *LLDAS*

Number of patients achieving a LLDAS at Week 36 will be presented by treatment group (Statistical table 14.2.18). It is defined as:

- SLEDAI-2K ≤ 4 , with no activity in major organ systems (renal, CNS, cardiopulmonary, vasculitis, fever) and no haemolytic anaemia or gastrointestinal activity
- No new features of lupus disease activity compared with the previous assessment (New feature is defined as any BILAG item recorded as "new" (modality 4) at Week 36)
- Physician global assessment (PGA, scale 0–3) ≤ 1
- Current prednisolone (or equivalent) dose ≤ 7.5 mg daily (this criterion will be identified by medical review)
- Well tolerated standard maintenance doses of immunosuppressive drugs and approved biological agents, excluding investigational drugs (this criterion will be identified by medical review)

Statistical Analysis Plan

Study Name: IFN-K-002

SAP version & date: v4, 18/Jun/2018

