14.2.5.11	Secondary efficacy analysis - Composite SRI-4 response (CS 7.5 mg) - Logistic regression model with status of IFN α neutralizing antibodies (positive/negative) at Week 36 as dependent variable				X	
14.2.6.1	Secondary efficacy analysis - SRI-6 response at Week 36			X		
14.2.6.2	Secondary efficacy analysis - SRI-6 response at Week 36 - Logistic regression model			X		

Statistical Analysis Plan

Study Name: IFN-K-002

SAP version & date: v4, 18/Jun/2018

Number	Title	Screened	SAF	FAS	PP	Other
14.2.7.1	Secondary efficacy analysis - SRI-8 response at each visit			X		
14.2.7.2	Secondary efficacy analysis - SRI-8 response at Week 36 - Logistic regression model			X		
14.2.8.1	Secondary efficacy analysis - SRI-10 response at each visit			X		
14.2.8.2	Secondary efficacy analysis - SRI-10 response at Week 36 - Logistic regression model			X		
14.2.9	Secondary efficacy analysis - SLEDAI response at week 36			X		
14.2.10.1	Secondary efficacy analysis - SLEDAI-2K scores - Value at each visit			X		
14.2.10.2	Secondary efficacy analysis - SLEDAI-2K scores - Change from baseline			X		
14.2.11	Secondary efficacy analysis - BILAG - Shift table			X		
14.2.12	Secondary efficacy analysis - BILAG global score			X		
14.2.13	Secondary efficacy analysis - SELENA-SLEDAI - Mild, moderate or severe SLE flare			X		
14.2.14.1	Secondary efficacy analysis - SELENA-SLEDAI score - Value at each visit			X		
14.2.14.2	Secondary efficacy analysis - SELENA-SLEDAI score - Change from baseline			X		
14.2.15.1	Secondary efficacy analysis - SLICC/ACR-DI score - Value at each visit			X		
14.2.15.2	Secondary efficacy analysis - SLICC/ACR-DI score - Change from baseline			X		
14.2.16.1	Secondary efficacy analysis - CLASI - Total activity score - Value at each visit			X		
14.2.16.2	Secondary efficacy analysis - CLASI - Total activity score - Change from baseline			X		
14.2.17.1	Secondary efficacy analysis - CLASI - Total damage score - Value at each visit			X		
14.2.17.2	Secondary efficacy analysis - CLASI - Total damage score - Change from baseline			X		
14.2.18	Secondary efficacy analysis - LLDAS			X		
14.2.19	Immunogenicity analysis - Anti-IFN α binding antibody titers - Positive antibody response over time				X	
14.2.20	Immunogenicity analysis - Log-transformed dilution titers for anti-IFN α binding antibodies				X	

Statistical Analysis Plan

Study Name: IFN-K-002

SAP version & date: v4, 18/Jun/2018

Number	Title	Screened	SAF	FAS	PP	Other

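### The CLASI objective is limited to patients with skin lesions at baseline, but the planned Week 36 t-test uses the whole FAS without explanation

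*SAP*

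**What the plan says.** The objective names a population. Protocol 6.2 lists "The Cutaneous Lupus Erythematosus Disease Area and Severity Index (CLASI) in patients with cutaneous lesions at baseline" among the secondary objectives. The protocol synopsis and SAP 2.2.2 repeat the limit. CLASI is the only efficacy instrument in that list with a population limit.

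The endpoint and the analysis do not carry it forward:

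- Protocol 13.3.1 and SAP 4.1.2.1 give CLASI as an endpoint for all patients.
- Protocol 13.9.3 plans a t-test and names no subset.
- SAP 5.2.4.3 sets the default: "Secondary efficacy analyses will be performed on the FAS population except if otherwise specified".
- SAP 5.2.4.3.6 specifies nothing else: "Total activity score and Total damage score at each visit and change from baseline by treatment group will also be presented". It adds a t-test on the Week 36 changes.
- SAP 3.3.1 defines the FAS as every randomized patient with at least one dose, with no skin criterion.
- The table list in SAP 10.1 places tables 14.2.16.1 to 14.2.17.2, for example "Secondary efficacy analysis - CLASI - Total activity score - Change from baseline", in the FAS column.
- SAP 5.3.8 defines no subgroups, and SAP section 7 does not mention CLASI among the changes from the protocol.

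Neither document defines what counts as a cutaneous lesion at baseline.

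**The concern.** A trial run to this plan would report a CLASI difference for a population other than the one named in its objective. A patient whose baseline activity score is 0 can stay at 0 or worsen, but cannot improve. If such patients show no treatment effect, averaging them in pulls the estimated difference toward zero, and a reader who sets the result beside the objective would take it for the effect in patients with skin disease.

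A second issue is timing. Because baseline lesions are undefined, a lesional analysis added later would require the definition to be chosen with the data in hand.

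**Working it through.** **1. Do patients without lesions enter the test?** Yes. Inclusion criteria 2 and 3 (protocol 8.3.1) require SLEDAI of at least 6 and BILAG A or B activity in any system, so skin disease is not required. Protocol Table 1 schedules CLASI for everyone at Weeks 0, 12, 24 and 36. Under SAP 5.3.2 a CLASI score is missing only when items are missing, so a score of 0 is an observed value and stays in.

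**2. The plan's own power figure.** The only continuous-endpoint figure is for the gene signature: difference 32.6, SD 68, 80 per arm, two-sided 5%. The noncentral t gives 85.4% (stated: 85%), and 160/0.9 = 177.8 gives 178 enrolled (stated: 178). No effect size, SD, lesional share or power is given for CLASI. All CLASI inputs below are therefore assumptions, apart from 80 per arm and the two-sided 5% level.

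**3. Dilution.** Let q be the share with lesions and Δ the lesional difference, with no treatment effect in the others. The whole-FAS difference is q × Δ. For Δ = 2.0 points:

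- q = 0.8: 1.6
- q = 0.6: 1.2
- q = 0.5: 1.0

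**4. Power if non-lesional change is exactly 0.** With lesional mean change m and SD s, the whole-FAS variance in an arm is q·s² + q(1−q)·m². The lesional test uses 80q per arm. Worked case, q = 0.6, changes −3 (placebo) and −5 (IFN-K), s = 4:

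- Placebo variance: 0.6×16 + 0.24×9 = 11.76. IFN-K variance: 0.6×16 + 0.24×25 = 15.60.
- Whole FAS: 1.2/√(27.36/80) = 2.05, power 53%.
- Lesional subset, 48 per arm: 2.0/(4×√(2/48)) = 2.45, power 68%.

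The same calculation at q = 0.6 and Δ = 2, varying the other inputs:

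| Placebo vs IFN-K change | SD | Lesional subset | Whole FAS |
|---|---|---|---|
| −3 vs −5 | 4 | 68% | 53% |
| −1 vs −3 | 4 | 68% | 63% |
| 0 vs −2 | 4 | 68% | 66% |
| −3 vs −5 | 6 | 37% | 32% |

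The loss runs from about 2 to 15 percentage points. Its main driver is the improvement common to both arms relative to the SD. When that is small, the zeros reduce the variance almost enough to offset the smaller difference.

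**5. Wider range.** Fix the lesional test at 80% power. Let placebo change in lesional patients run from 0 to −1 SD, and let the SD of change in non-lesional patients run from 0 to 0.5 lesional SD. Whole-FAS power is then 79.0% to 66.3% at q = 0.8, 77.5% to 53.7% at q = 0.6, and 74.4% to 42.0% at q = 0.4. Over all these shares the loss is about 1 to 38 points.

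**6. Reversal.** Take q = 0.6, lesional changes −1 vs −3 and SD 4. Let non-lesional patients change by +0.4 on placebo and 0 on IFN-K, with SD 1.

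- Difference: 0.6×2 + 0.4×0.4 = 1.36.
- Placebo variance: 0.6×(16+1) + 0.4×(1+0.16) − 0.44² = 10.47.
- IFN-K variance: 0.6×(16+9) + 0.4×1 − 1.8² = 12.16.
- Whole-FAS power is 72%, against 68% in the subset.

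**The case against.** The strongest reply is that the whole FAS may be a reasonable choice. Patients without lesions cannot improve, but they can develop lesions. Corticosteroid tapering is encouraged and then mandatory (protocol Table 4), so new skin activity is possible. A whole-FAS analysis captures an effect on new lesions, and a lesional subset discards it. Step 6 shows that this can outweigh the dilution. This stands as a reason to keep the whole-FAS result. It does not explain the mismatch, because the objective asks about patients who already have lesions and neither document says the wider population was chosen to capture prevention.

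The floor argument also does not carry over to the damage score. Protocol 11.6 describes CLASI damage as permanent, so little improvement is expected in anyone. That stands: the dilution in step 3 is a statement about activity, and damage needs its own rule.

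A simple flag of activity above 0 would not reproduce the objective either. Under protocol Appendix 7 the activity total also includes mucous membrane and alopecia items, so the flag would admit patients with no skin lesion and miss those whose only lesions are damage. This stands and shapes the fix.

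Finally, CLASI is one of several secondary endpoints. It carries no power claim and lies outside both the two-step test sequence (SAP 5.3.5) and the success rule (SAP 5.2.4.1). All CLASI data will be listed, so a subset could be produced later. That limits the impact, but a subset defined after unblinding is weaker evidence than a prespecified one.

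**Conclusion.** The mismatch between objective and analysis is certain from the text and occurs in both documents. Dilution of the activity difference to q × Δ follows if patients without baseline lesions show no treatment effect. That condition is plausible, but the documents do not establish it.

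A reader might infer that the whole-FAS analysis necessarily loses power. The documents do not support that: they give no CLASI mean, SD or lesional share. At 60% with lesions and a 2-point difference the loss is about 2 to 15 points across the cases shown. Other shares and noisier non-lesional scores widen this to about 1 to 38 points, and a modest preventive effect turns it into a gain.

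The sample size, the co-primary endpoints and the success rule are unaffected. This is a secondary-endpoint correction worth making because it is cheap and can be prespecified.

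**What to change.** Before unblinding:

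1. Define baseline cutaneous lesions from the Visit 2 CLASI. For the activity score, one option is a non-zero erythema or scale/hypertrophy item at any site. State whether the mucous membrane and alopecia items count. Give a separate, explicit rule for the damage score.
2. Make the Week 36 t-test in that FAS subset the main CLASI analysis, and keep the whole-FAS result as supportive.
3. Align SAP 4.1.2.1, 5.2.4.3.6 and 5.3.8 and tables 14.2.16.1 to 14.2.17.2. Record in SAP section 7 that protocol 13.3.1 and 13.9.3 carried no limit. If the whole FAS was intended, state and justify it there instead.

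The cost is a short definition, a subset flag and revised table headers, using data already collected. The downside is a smaller n for the main CLASI test, and any effect on new lesions will show only in the supportive analysis.

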10.9.13 Early Termination Visit

If the patient exits the study before Week 36 after having received at least one injection of study product, the following assessments and evaluations will be carried out whenever possible:

- Collect quality of life:
 - SF-36 health survey score
 - FACIT fatigue score
- Assess disease activity scores:
 - SLEDAI-2K
 - PGA
 - BILAG-2004 index
 - SELENA-SLEDAI flare index
 - SLICC/ACR-DI
 - Count of Tender & Swollen Joints
 - Joint Pain VAS
 - CLASI
- Record all AEs
- Record concomitant medication
- Perform complete physical examination, including body temperature and weight
- Measure vital signs – brachial pulse and blood pressure to be taken after 3 minutes of rest in a supine position

- Perform a gynecological examination, including examination of the cervix, cervical swabbing for cytological examination (PAP smear) and detection of high risk HPV (by RT qPCR)
- Perform a 12-lead ECG
- Obtain chest X-Ray where allowed by local regulation
- Perform urine pregnancy test for female patients of childbearing potential
- Perform urinalysis, including dipstick and microscopic examination
- Obtain blood sample for:
 - Hematology, coagulation (INR, PT, PTT, fibrinogen), biochemistry (complete)
 - Lymphocytes count (Total, CD4+, CD8+)
 - Anti-IFN α binding antibodies
 - Anti-KLH binding antibodies
 - Anti-IFN α neutralizing antibodies
 - Neutralizing Anti-IFN α antibodies towards IFN α subtypes
 - Anti-IFN α and anti-KLH antibody isotyping
 - IFN β cross-neutralization
 - Anti-dsDNA antibodies
 - ANA
 - Other autoantibodies (anti-Sm, anti-RNP, anti-SSA/Ro, anti-SSB/La, anti-cardiolipin and anti- β_2 -glycoprotein I antibodies)
 - Inflammatory markers (C3, C4, CH50)
 - IFN gene signature (by Affymetrix)

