5.2.4.5 Exploratory analyses

The following analysis will be performed on the FAS population except if otherwise specified.

5.2.4.5.1 **PGA scores**

PGA score at each visit and change from baseline by treatment group will be presented. (Statistical tables 14.2.28.1 to 14.2.28.2)

All PGA data will be listed in Listing 16.2.6.10.

5.2.4.5.2 **SLE flares**

Time to first SLE flare in patients will be analyzed using a cox regression model.

The first model will be adjusted on treatment group.

The second model will be performed only on patients IFN-K treated and will be adjusted on presence/absence of neutralizing antibodies. (Statistical tables 14.2.29.1 to 14.2.29.2)

5.2.4.5.3 **28-Tender and Swollen Joint Counts (SJC)**

28-Tender and Swollen Joint Counts and Joint Pain VAS at each visit and change from baseline will be presented. The changes at Week 36 will be analyzed using a t-test. (Statistical tables 14.2.30.1 to 14.2.32.2).

28-Tender and Swollen joint counts data will be listed in Listing 16.2.6.11, and joint Pain VAS data in Listing 16.2.6.12.

5.2.4.5.4 **Treatment failure**

- Proportion of treatment failure will be analyzed using frequency table methods. Patients will be considered as treatment failure if they receive more than 5 mg prednisone equivalent/day at any time between Week 24 (Visit 9) and Week 36 (Visit 12) or if their CS dose is increased above the Week 24 level is recorded (this criterion will be identified by medical review) (Statistical table 14.2.33)

5.2.4.5.5 **SF-36**

Statistical Analysis Plan

Study Name: IFN-K-002

SAP version & date: v4, 18/Jun/2018

Physical Component Summary (PCS) and Mental Component Summary (MCS) scores at each visit and change from baseline will be presented. The changes at Week 36 will be analyzed using a non-parametric Wilcoxon rank sum test (Statistical tables 14.2.34.1 to 14.2.35.2). If one is statistically significant then the individual domain scores will also be described.

In addition, number of patients with clinically meaningful improvements \geq Minimum Clinically Important Differences (MCID) of 2.5 points for summary and 5.0 points for domain scores between baseline and Week 36 will be presented. (Statistical tables 14.2.36 to 14.2.37)

All SF-36 data will be presented in Listing 16.2.6.13.

5.2.4.5.6 **FACIT**

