Total scores at each visit and change from baseline by treatment group will be presented. The change at Week 36 will be analyzed using a t-test. (Statistical tables 14.2.39.1 to 14.2.39.2)

All FACIT data will be presented in Listing 16.2.6.14.

5.2.4.5.7 **Autoantibodies**

The levels of auto-antibodies (ANA, anti-dsDNA, anti-Smith antigen [anti-Sm], anti-RNP, anti-SSA/Ro, anti-SSB/La, anti-cardiolipin, and anti- β 2-glycoprotein I antibodies) will be described at each visit by treatment group. Change from baseline by treatment group will be presented for quantitative parameters. For anti-dsDNA, the change at Week 36 will be analyzed using a t-test. (Statistical tables 14.2.40.1 to 14.2.40.2). These analyses will be performed on the PP population.

All auto-antibodies data will be listed in Listing 16.2.6.15.

5.2.4.5.8 **Biomarkers**

The biomarkers (C3, C4, CH50) at each visit and change from baseline by treatment group will be presented. (Statistical tables 14.2.41.1 to 14.2.41.2). For C3 the change at Week 36 will be analyzed using a t-test. These analyses will be performed on the PP population.

All biomarkers data will be listed in Listing 16.2.6.16.

5.2.4.5.9 **Anti-IFN α and anti-KLH antibody isotyping**

Descriptive analysis will be performed on Anti-IFN α and anti-KLH antibody isotyping data. (Statistical table 14.2.42)

All corresponding data will be listed in Listing 16.2.6.17.

5.2.4.5.10 **Anti-Hemagglutinin antibody response following influenza vaccination**

Seroconversion (four folds increase in antibody titers post-vaccination) and seroprotection (HIA antibody titers \geq 1:40 post-vaccination) will be presented by treatment group for each visit. In addition, results by visit will be presented according to status of anti-IFN α neutralizing antibodies (positive/negative) at the corresponding visit (Statistical table 14.2.43). These analyses will be performed on the FAS population, only on patients vaccinated with seasonal Flu and with sample at baseline and post-baseline.

Statistical Analysis Plan

Study Name: IFN-K-002

SAP version & date: v4, 18/Jun/2018

All corresponding data will be listed in Listing 16.2.6.18.

5.2.4.5.11 ***Neutralizing Anti-IFN α antibodies towards IFN α subtypes***

Descriptive analysis will be performed on Neutralizing Anti-IFN α antibodies towards IFN α subtypes data. (Statistical table 14.2.44)

All corresponding data will be listed in Listing 16.2.6.19.

5.2.4.5.12 ***Other***

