5.3.2 Handling of Dropouts or Missing Data

Missing data in efficacy analysis:

For the primary endpoint – IFN gene signature – the last available value either at Visit 9 or 12 will be used for the ANCOVA model.

Missing items in questionnaires:

- SLEDAI-2K and SELENA SLEDAI:
 - At visit 6, 9 and 12 (SLEDAI-2K) or at visit 9 and 12 (SELENA-SLEDAI flare index) respectively, for descriptors “Urinary casts, Hematuria, Proteinuria, Pyuria, Low complement, Increased DNA binding, Thrombocytopenia, Leukopenia”, if value “Not done” is recorded because of no urinary/lab results available, corresponding descriptor from previous visit will be used
 - Other missing data should be considered as not present (protocol rule: items should be recorded if the descriptor is present at the time of the visit or in the preceding 10 days)
- CLASI: missing data will not be replaced. The score will be considered as missing.
- SF-36: scores for each scale are calculated for respondents completing 50% or more of the items within a scale. Among these respondents, the value for any missing item is imputed as the mean value for non-missing items (John E. Ware)
- FACIT fatigue: if there are missing items, subscale scores can be prorated. This is done by multiplying the sum of the subscale by the number of items in the subscale, then dividing by the number of items actually answered. When there are missing data, prorating by subscale in this way is acceptable as long as more than 50% of the items were answered (e.g., a minimum of 4 of 7 items, 4 of 6 items, etc). (Facit Administration and Scoring Guidelines)
- BILAG: For renal BILAG change in renal function over the last four weeks: if previous renal function is not known it will be assumed to be normal and urinalysis will be given values of 0, serum creatinine will be given a value of 100 µmol/L and creatinine clearance (GFR) will be given a value of 100 mL/min. The results entered at the first assessment will be carried forward unless replaced by new values and they should be overwritten if no longer applicable (DA Isenberg). For other cases, score is calculated with the available data.

Statistical Analysis Plan

Study Name: IFN-K-002

SAP version & date: v4, 18/Jun/2018

Missing or incomplete dates:

For calculation / sorting / assignation based on dates (e.g., treatment emergent AEs, concomitant medications...), the following rules will apply:

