- The most conservative approach will be considered (i.e., if the onset date of an AE/concomitant medication is missing / incomplete, it will be assumed to have occurred during the study treatment phase (i.e., a TEAE for AEs) except when the partial onset date or other available data indicates differently (e.g., start date day missing, but month before the month of baseline date, or stop date before baseline date)).
- Medical history or disease diagnosis with missing/incomplete date will be assumed to have occurred before any study treatment except when the partial onset date or other available data indicates differently.
- Assignations based on dates will be reviewed and confirmed or infirmed during the data review meeting

No other missing data will be imputed, and all available efficacy and safety data will be included in data listings and tabulations.

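### The Week 36 tests of CLASI, SELENA-SLEDAI, joint counts, joint pain, FACIT and SF-36 drop patients without a Week 36 value, although earlier scores are collected and the set is labelled FAS

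*SAP*

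**What the plan says.** SAP 5.2.4.3 sets the population: "Secondary efficacy analyses will be performed on the FAS population except if otherwise specified". SAP 5.2.4.5 does the same for the exploratory scores. SAP 3.3.1 defines the FAS as randomized patients with at least one dose.

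The tests are all on the Week 36 change:

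- CLASI activity and damage (5.2.4.3.6): "The changes at Week 36 will be analyzed using a t-test". The SELENA-SLEDAI score (5.2.4.3.4) is treated the same way.
- Joint scores (5.2.4.5.3): "28-Tender and Swollen Joint Counts and Joint Pain VAS at each visit and change from baseline will be presented", followed by a t-test at Week 36.
- FACIT (5.2.4.5.6): "The change at Week 36 will be analyzed using a t-test".
- SF-36 PCS and MCS (5.2.4.5.5): "The changes at Week 36 will be analyzed using a non-parametric Wilcoxon rank sum test".

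SAP 5.3.2 has a missed-visit rule for the gene signature only: "the last available value either at Visit 9 or 12 will be used for the ANCOVA model". Its SLEDAI, SF-36 and FACIT rules repair missing items within an assessment that took place; incomplete CLASI scores stay missing. It then closes the list: "No other missing data will be imputed, and all available efficacy and safety data will be included in data listings and tabulations". SAP 5.4.3 analyses visits as entered unless the data-review meeting decides otherwise.

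The schedule (Protocol Table 1) has CLASI, joint counts, joint-pain VAS, SF-36 and FACIT at Weeks 0, 12, 24 and 36, and the SELENA-SLEDAI index at Weeks 0, 24 and 36. Protocol 10.9.13 repeats all of them, where possible, "If the patient exits the study before Week 36 after having received at least one injection of study product".

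**The concern.** A patient who leaves before Week 36 contributes nothing to these tests, even with Week 12 and Week 24 scores on file. The analysis set promises an answer for all dosed patients; the method answers for those measured at Week 36. If the two arms lose different numbers of patients, and those who leave are doing worse, the arm that loses more looks better than it was and the comparison is biased.

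The plan is also uneven. The gene signature has a carry-forward rule and a sensitivity MMRM (SAP 5.2.4.2), and the BILAG global score is tested on the last available value of Week 24 or Week 36 (SAP 5.2.4.3.3). The scores listed here have neither. The SAP's change history removed the other repeated-measures models for consistency, after noting that BICLA is meaningful only at Week 36. That reason does not carry over to scores measured at earlier visits.

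**Working it through.** **1. The plan's own figures.** Inputs (Protocol 13.1): difference 32.6, SD 68, 80 evaluable per arm, two-sided 5%, 10% dropout.

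- Power = Φ(32.6 / (68 × √(2/80)) − 1.96) = Φ(3.03 − 1.96) = 85.8%; the noncentral t gives 85.4%. The stated 85% is reproduced.
- Enrolment: 160 / 0.90 = 177.8, so 178, or 89 per arm. Reproduced.

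The documents give no power or dropout split for the scores at issue, so everything below rests on stated assumptions.

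**2. Loss of numbers alone.** At 10% dropout about 18 of 178 patients leave each test. Power with 89 against 80 per arm, from Φ(δ√(n/2) − 1.96), is 51.6% against 47.5% at δ = 0.3 SD, 76.1% against 71.6% at 0.4 SD, and 91.6% against 88.5% at 0.5 SD. This is an upper bound on what could be recovered.

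**3. Bias.** Let withdrawn patients be g SD worse than those measured at Week 36, with the same g in both arms, and let dP and dT be the placebo and IFN-K withdrawal fractions. Each arm's full mean equals its observed mean plus d × g, so the observed benefit is too small by g × (dP − dT). With 89 per arm, SE = √(1/(89(1−dP)) + 1/(89(1−dT))) ≈ 0.158 SD. Assume a true benefit of 0.45 SD and g = 0.5 to 1.0:

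| Placebo / IFN-K withdrawal | Bias (SD) | Share of 0.45 SD | Rejection if no true effect |
|---|---|---|---|
| 10% / 10% | 0 | 0 | 5% |
| 11.5% / 8.5% | 0.015-0.03 | 3-7% | see step 4 |
| 13% / 7% | 0.03-0.06 | 7-13% | 5-7% |
| 15% / 5% | 0.05-0.10 | 11-22% | 6-10% |
| 5% / 15% | −0.05 to −0.10 | 11-22% too large | 6-10% |

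Example for 15%/5% with g = 1: bias 0.10, z = 0.10/0.158 = 0.63, rejection = Φ(−1.96 + 0.63) + Φ(−1.96 − 0.63) ≈ 9.7%. Stronger selection in simulation takes this row to about 25% bias and 13% rejection; weaker selection shrinks it in proportion to g.

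**4. What split is plausible?** Simulate one withdrawal rule for both arms, driven by the last observed score: 89 per arm, about 10% withdrawal overall, between-visit correlation 0.5 or 0.7, logistic slope 0.5 to 2 per SD. With a true 0.45 SD effect the split comes out between about 10.5%/9.5% and 11.5%/8.5%. The estimate from patients with a Week 36 value is 0.42-0.45 (0-7% too small) and power is 79-81%. With no true effect the arms withdraw equally and rejection is 4.7-5.3%.

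**5. What a likelihood model recovers.** Simulate correlations of 0.7 between adjacent visits and 0.6 between Weeks 12 and 36, with withdrawal after Week 24 depending on the Week 24 score. With about 19%/4% withdrawal and a true difference of −0.45 SD, patients with a Week 36 value give −0.37 and the likelihood estimate using Weeks 12 and 24 gives −0.45. At about 10%/7% the two are −0.44 and −0.45.

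**The case against.** The strongest objection is that the bias is probably small. A reader might infer that patients who flare, need prohibited treatment or stop study product are the ones dropped. The documents do not support that. Protocol 10.6.3 and 10.7.2 ask patients who stop study product to continue procedures to Week 36, and flare is not on the product-discontinuation list. Recording a flare as an adverse event (Protocol 12.1.1) is a reporting rule, not a reason to leave. What is lost is study withdrawals and missed Week 36 visits. This stands.

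A reader might also infer a false-positive rate of twice the nominal 5%. That needs roughly three times as much withdrawal on placebo although the arms' scores are identical, so it needs an arm-specific mechanism. The documents give none, and both arms receive the same adjuvant. This stands too.

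Two further points limit the scope. The BILAG global score already uses a last available value, and values at each visit are tabulated by arm, so withdrawn patients' earlier scores are reported.

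The data-review meeting could assign early-termination values to visits, but no rule is specified in advance. Agreement of the t-tests with Protocol 13.9.3 and 13.9.6 does not settle who is in them. The objection reduces the size of the problem; it does not supply the missing rule.

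**Conclusion.** The point holds for CLASI activity and damage, the SELENA-SLEDAI score, 28-joint tender and swollen counts, joint-pain VAS, FACIT and SF-36 PCS/MCS: tests labelled FAS include only patients with a Week 36 value.

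The size is uncertain and probably modest. There is no bias at 10%/10%, about 0-7% of a 0.45 SD effect under one score-driven rule for both arms, and about 11-25% with null rejection of about 6-13% only under an assumed 15%/5% split. The effect size, the split and the strength of selection are assumptions; the documents give only 10% overall.

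It would go too far to say that every continuous score is affected or that type I error is materially inflated in this trial. Study success rests on the two co-primary endpoints (SAP 5.2.4.1 and 5.3.5), so the stake is the reliability of supportive results. Priority is low to moderate. Since the split is unknown before unblinding, the method should be settled before then.

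**What to change.** - **Scores tested by t-test** (SAP 5.2.4.3.4, 5.2.4.3.6, 5.2.4.5.3, 5.2.4.5.6): make the Week 36 contrast from an MMRM on all scheduled post-baseline visits the main test. Use Weeks 12, 24 and 36, or Weeks 24 and 36 for SELENA-SLEDAI. Specify categorical visit, treatment-by-visit, baseline score and unstructured covariance; SAP 5.3.1 already asks any MMRM to carry the baseline value and the minimization factors. Keep the t-test as supportive.
- **SF-36 PCS/MCS** (5.2.4.5.5): keep the Wilcoxon test and add the MMRM as a pre-specified sensitivity analysis.
- **Early-termination values:** use one only when it falls within the protocol window (Protocol Table 5) of a scheduled visit that has no value. Do not move it forward to Week 36.

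The cost is SAP wording and a few models on data already collected. The downside is that the MMRM assumes missing at random and approximate normality. It corrects only the part of the bias that the observed scores explain.
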